## **8.0 STATISTICAL ANALYSIS PLAN**

### **8.1 Statistical Analysis Plan Summary**

This section contains a brief summary of the statistical analyses for this trial. Full detail is in the Statistical Analysis Plan (SAP) (Section 8.2).

The primary population of statistical analysis is cohort 2 and the analysis plan described in this section will be conducted in cohort 2. Data from extension period will be excluded from the analyses of Cohort 2.   

#### **8.1.1 Efficacy Analyses**

The primary endpoints, primary analysis population, and statistical method that will be employed for the efficacy analyses are presented in [Table 24](#) below.

The primary efficacy endpoint is the overall response assessed by CAC. The overall response rates (the proportion of subjects with “success” assessment [see Section 8.2.3.3]) for invasive aspergillosis at Day 42 and for chronic pulmonary aspergillosis (chronic progressive pulmonary aspergillosis and simple pulmonary aspergilloma) at Day 84 and their 95% confidence intervals will be computed by treatment. Subjects with solid oral tablet, IV solution and switch from IV solution to solid oral tablet for the MK-5592 treatment arm will

be pooled for the analyses due to the fact that it reflects clinical practice and the different routes of administration achieve targeted plasma concentration level of MK-5592. Likewise, subjects with oral tablet, IV solution and switch from IV solution to oral tablet for the Voriconazole treatment arm will be pooled for the analyses.

The overall response for the subjects with fusariosis and zygomycosis will be listed for MK-5592 treatment arm since the enrollment of these infections will be very limited.

Table 24 Analysis Strategy for Primary Efficacy Endpoint

Endpoint/Variable (Description, Timepoint)	Statistical Method	Analysis Population	Missing Data Approach
Overall response rates for invasive aspergillosis at Day 42 and for chronic pulmonary aspergillosis at Day 84	95% CI with Clopper-Pearson Exact Method	FAS	Carry Forward

### 8.1.2 Safety Analyses

The All-Subjects-as-Treated (ASaT) population will be used for the analysis of safety data in this study. The ASaT population consists of all randomized patients who received at least one dose of study treatment. Invasive aspergillosis and chronic pulmonary aspergillosis will be pooled for the analyses but subject with fusariosis and zygomycosis will be separately evaluated. In this study, the prespecified events of interest (Tier-1 events) are not defined.

### 8.1.3 Power and Sample Size

This study initially planned to enroll a total of 90 subjects but due to the modification in protocol such as inclusion and exclusion criteria, an additional 90 subjects will be enrolled as cohort 2, [REDACTED] The cohort 2 will enroll subjects as initially planned for this protocol:

This study will randomize 60 subjects into the MK-5592 treatment arm and 30 into the Voriconazole treatment arm. A total number of 90 subjects were set with consideration of recruitment feasibility based on the past experiences (See Section 8.2.7 for details). A total of 90 subjects include those with all aspergillosis for safety analyses, and among them 15 subjects with invasive aspergillosis as a target number will be enrolled. Subjects with fusariosis and zygomycosis will be assigned to the MK-5592 treatment arm and their target number of recruitment is not set.

### 8.1.4 Interim Analyses

Formal interim analyses are not planned in this study. Safety and PK data will be reviewed by the sponsor on an ongoing basis. No alpha adjustment is needed since no hypothesis is tested in this study.

## **8.2 Statistical Analysis Plan**

The primary population of statistical analysis is cohort 2 and the analysis plan described below will be conducted in cohort 2. Data from extension period will be excluded from the analyses of Cohort 2. Safety and PK data in cohort 1 will be separately summarized from cohort 2.

### **8.2.1 Responsibility for Analyses/In-House Blinding**

The statistical analysis of the data obtained from this study will be the responsibility of the Clinical Biostatistics department of the SPONSOR.

This trial is being conducted as an open-label study, i.e., patients, investigators, and SPONSOR personnel will be aware of patient treatment assignments after each patient is enrolled and treatment is assigned.

The Clinical Biostatistics department or designee will generate the randomized allocation schedule for study treatment assignment. Randomization will be implemented by registration center.

This trial is being conducted as an open-label study but the diagnosis and overall response will be assessed by CAC in a blinded manner based on data with masked information such as treatment assignment.

### **8.2.2 Hypotheses/Estimation**

Objectives and hypotheses of the study are stated in Section 3.0. The hypothesis is not set since the main objective of this study is safety assessment.

### **8.2.3 Analysis Endpoints**

Efficacy and safety endpoints are listed below.

#### **8.2.3.1 Efficacy Endpoints**

##### **8.2.3.1.1 Primary Efficacy Endpoint**

The Primary efficacy endpoint is the overall response for invasive aspergillosis at Day 42 and for chronic pulmonary aspergillosis at Day 84 assessed by CAC.

[figure not shown]
##### **8.2.3.1.2 Secondary Efficacy Endpoints**

The following endpoints assessed by CAC will be secondary efficacy endpoints:

- Overall response for invasive aspergillosis at Day 84
- Overall response for chronic pulmonary aspergillosis (chronic progressive pulmonary aspergillosis and simple pulmonary aspergilloma) at Day 42

- Overall response for all aspergillosis [invasive aspergillosis and chronic pulmonary aspergillosis (chronic progressive pulmonary aspergillosis and simple pulmonary aspergilloma)] at EOT
- Overall response for fusariosis and zygomycosis at Day 42 and Day 84
- Clinical response for invasive aspergillosis and chronic pulmonary aspergillosis (chronic progressive pulmonary aspergillosis and simple pulmonary aspergilloma) at Day 42 and Day 84
- Radiological response for invasive aspergillosis and chronic pulmonary aspergillosis (chronic progressive pulmonary aspergillosis and simple pulmonary aspergilloma) at Day 42 and Day 84
- Mycological response for invasive aspergillosis and chronic pulmonary aspergillosis (chronic progressive pulmonary aspergillosis and simple pulmonary aspergilloma) at Day 42 and Day 84

In addition, overall response for invasive aspergillosis at Day 42 and for chronic pulmonary aspergillosis at Day 84 assessed by investigators/sub-investigators will be evaluated as a secondary efficacy endpoint.

### 8.2.3.2 Safety Endpoints

Refer to Section 7.0 for safety endpoints.

### 8.2.3.3 Derivations of Efficacy Endpoints

The overall response will be assessed by CAC using clinical, radiological and mycological response data. The data for assessing the overall response and criteria of efficacy judgment are presented in the [Table 25](#) and criteria for overall response is presented in Section 4.2.3.1.

Data will be submitted to CAC with masked Information such as treatment assignment and CAC will assess the overall response in a blinded manner.

**Table 25 The Data for Assessing the Overall Response and Criteria of Efficacy Judgment**

Disease Category	Information for assessing the overall response	Efficacy Assessment	
		Success	Failure
Invasive aspergillosis †	Clinical response Radiological response Mycological response	Complete Response Partial Response	Stable Response Progression of disease Unable to determine
Chronic pulmonary aspergillosis (chronic progressive pulmonary aspergillosis and simple pulmonary aspergilloma)	Clinical response Radiological response	Favorable Response	Stable Response Progression of disease Unable to determine
Fusariosis and zygomycosis	Clinical response, Radiological response and Mycological response Or Clinical response and Mycological response	Complete Response Partial Response	Stable Response Progression of disease Unable to determine

†Subjects with possible invasive aspergillosis may also be enrolled into the study with further evaluation of proven or probable invasive aspergillosis, which must be confirmed by 7 days post-randomization to be included in the FAS analysis.

## 8.2.4 Analysis Populations

### 8.2.4.1 Efficacy Analysis Populations

The Full Analysis Set (FAS) population will serve as the primary population for the analysis of efficacy data in this study. The FAS for a given endpoint consists of all randomized subjects in cohort 2 who:

- Diagnosed as target disease (proven or probable) by CAC
- Receive at least one dose of study treatment
- Have a baseline observation for the analysis endpoint

Subjects with possible invasive aspergillosis may also be enrolled into the study with further evaluation of proven or probable invasive aspergillosis, which must be confirmed by 7 days post-randomization to be included in the FAS analysis.

An Intention To Treat (ITT) population is defined as all randomized subjects in cohort 2 who received at least one dose of study treatment, and the analysis of the primary efficacy endpoint will be performed.

A supportive analysis using the Per-Protocol population in cohort 2 will be also performed for the primary efficacy endpoint. The Per-Protocol population excludes patients due to important deviations from the protocol that may substantially affect the results of the primary efficacy endpoint. Potential violations that may result in the exclusion of a patient from the Per-Protocol population include:

- Subjects with cases that affect the results of the primary efficacy endpoint, confirmed by CAC

The final determination on protocol violations, and thereby the composition of the Per-Protocol population, will be made prior to the final lock of the database and will be documented in a separate memo.

Patients will be included in the treatment group to which they are randomized for the analysis of efficacy data using both the FAS, ITT and Per-Protocol populations. Details on the approach to handling missing data are provided in Section 8.2.5.1.4.

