**Table 14 Trial Treatment**

Drug	Dose	Dose Frequency	Route of Administration	Regimen/Treatment Period	Use
MK-5592 (any one of oral tablet or IV solution must be selected)					
oral tablet	300 mg	QD (BID on Day 1)	Oral	84 days as a general rule	deep-seated fungal infection
IV solution	300 mg	QD (BID on Day 1)	Central intravenous		deep-seated fungal infection
Voriconazole (any one of oral tablet or IV formulation must be selected)					
oral tablet	200 mg (300 mg on Day 1)	BID	Oral	84 days as a general rule	deep-seated fungal infection
IV formulation	4 mg/kg(6 mg/kg on Day 1)	BID	intravenous		deep-seated fungal infection
If formulation is switched during the study, loading dose must not be administered again. From the date of switching formulation, maintenance dose administration should be continued.					

Trial treatment should begin on the day of randomization or as close as possible to the date on which treatment is allocated/assigned.

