### **5.2.3 Trial Blinding/Masking**

This is an open-label trial; therefore, the Sponsor, investigator and subject will know the treatment administered.

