11. At the switching formulation (from IV to PO), investigator must evaluate the overall response (including clinical response, radiological response, and mycological response). Data conducted on the day of switching formulation or preceding day can be used as an overall response at the switching formulation. In case that subject who started using oral formulation cannot continue to receive the oral formulation during the treatment, investigator must evaluate the overall response at that time and conduct the discontinuation procedure [However, if the subject is a patient with zygomycosis and joins the extension period, the switch of the formulation(iv↔tablet) could be done based on the subject's condition but dose modification of MK-5592 must not be allowed and the investigator does not need to evaluate the overall response at the timing of switching the formulation].
12. Weight measurement and Treatment Allocation may be conducted between Day -1 and Day 1. Treatment allocation and weight measurement should be conducted on the same date. Weight used for treatment allocation should be considered as basis of the dosing calculation. When conducting the Visit 2 weight measurement on Day -1, weight measurement does not need to be repeated on Day 1.
13. As a general rule, treatment duration of all disease is 84 days (77-84 days with considering the treatment allowance). At the EOT (completion and discontinuation) visit before the transition to the extension period, procedure other than dose administration should be conducted within EOT +2 days. At the end of treatment or discontinuation, procedure at EOT should be conducted before starting other systemic antifungal therapy[However, if the subject is a patient with zygomycosis and joins the extension period, procedure at visit 12/EOT does not need to be conducted at the last dose of MK-5592 therapy in the extension period].
14. Informed Consent could be obtained prior 28 days of Day 1.
15. Urine pregnancy testing can be conducted. Even though urine pregnancy testing is conducted, serum pregnancy testing should be conducted as a screening testing.

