#### **8.2.4.2 Safety Analysis Populations**

The All-Subjects-as-Treated (ASaT) population will be used for the analysis of safety data in this study. Randomized subjects with invasive aspergillosis and chronic pulmonary aspergillosis (chronic progressive pulmonary aspergillosis and simple pulmonary aspergilloma) will be pooled for the analyses but subjects with fusariosis and zygomycosis, not randomized subjects, will be separately evaluated. The ASaT population consists of all randomized subjects in cohort 2 who received at least one dose of study treatment. Subjects will be included in the treatment group corresponding to the study treatment they actually received for the analysis of safety data using the ASaT population.

At least one laboratory or vital sign measurement obtained subsequent to at least one dose of study treatment is required for inclusion in the analysis of each specific parameter. To assess change from baseline, a baseline measurement is also required.

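### In this open-label trial the population labelled ITT requires a dose, so no visible efficacy population contains all randomised subjects and the supportive check is weakened

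*Combined protocol and SAP*

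**What the plan says.** Section 8.2.4.1 defines three efficacy populations.

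- **FAS (primary).** Randomised cohort 2 subjects with proven or probable disease according to the adjudication committee and a baseline observation, who also "Receive at least one dose of study treatment".
- **ITT (supportive).** "An Intention To Treat (ITT) population is defined as all randomized subjects in cohort 2 who received at least one dose of study treatment". Subjects are analysed as randomised.
- **Per-Protocol (supportive).** Excludes subjects with important deviations.

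Section 8.2.4.2 gives the safety set the same membership rule as ITT: "The ASaT population consists of all randomized subjects in cohort 2 who received at least one dose of study treatment". Only the grouping differs, since safety is analysed as treated.

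On blinding, Section 5.2.3 states: "This is an open-label trial; therefore, the Sponsor, investigator and subject will know the treatment administered". Section 8.2.1 fixes the moment of knowledge. It names patients and investigators as well as sponsor staff, and says that "SPONSOR personnel will be aware of patient treatment assignments after each patient is enrolled and treatment is assigned".

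On timing, the text under Table 14 says: "Trial treatment should begin on the day of randomization or as close as possible to the date on which treatment is allocated/assigned". Footnote 12 of the flow chart (Section 6.0) adds: "Weight measurement and Treatment Allocation may be conducted between Day -1 and Day 1".

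Section 8.2.5.1.4 scores a subject in FAS or ITT as a failure when there are no data after treatment. Table 26 lists ITT as a supportive point estimate for the primary efficacy endpoint.

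**The concern.** A dosing condition does little harm when nobody knows the allocation, because the decision to start cannot then depend on the arm. Here it can. The documents themselves show differences between the arms that could bear on the decision: voriconazole is already approved in Japan (Section 4.1.1), some drug prohibitions apply after randomisation to one arm only (Table 13, notes a to c), and the intravenous routes differ (Table 14). Consent may be withdrawn at any time (Section 5.8).

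The primary FAS analysis already selects after randomisation, on adjudicated diagnosis and on dosing. ITT would normally be the analysis free of such selection. As defined, it lifts the diagnosis and baseline conditions but keeps the dosing condition. Agreement between FAS and ITT would therefore say nothing about subjects who never started, while a reader of the report would take the label to mean all randomised subjects. Blinded adjudication does not help, because undosed subjects are removed by the population rule before any response is analysed.

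**Working it through.** **Populations side by side**

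| Set | Dose required | Other conditions | Grouping |
|---|---|---|---|
| FAS | yes | adjudicated diagnosis, baseline observation | as randomised |
| ITT | yes | none | as randomised |
| Per-Protocol | no data-free subjects (Section 8.2.5.1.4) | no important deviations | as randomised |
| Safety (ASaT) | yes | none | as treated |

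No row holds an undosed subject with a scored outcome. Section 8.2.5.1.3 is redacted, so an exploratory analysis there cannot be excluded, but Section 8.2.4.1 defines no set that would support one.

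**The plan's own figures.** Section 8.2.7 gives precision, not power. Clopper-Pearson lower limits for 36/60 and 48/60 come out at 46.5% and 67.7%, as stated. Miettinen-Nurminen half-widths of 14.6, 16.1 and 17.9 points also reproduce, the middle one using 9/60 v 4/30. These figures do not depend on the ITT definition.

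**Inputs for the size**

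- Cohort 2 targets: 60 MK-5592 and 30 voriconazole (Sections 8.1.3 and 8.2.7).
- Response rates of 60% and 80%: the planning values in Section 8.2.7, applied here to both arms.
- Invasive aspergillosis target of 15 (Section 8.2.7). Assuming a 2:1 split, this is about 10:5, which leaves 60 − 10 = 50 and 30 − 5 = 25 with chronic pulmonary aspergillosis.
- Undosed subjects *u*: not given in the documents. Assumed range 0 to 3, in one arm only.

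**Formula.** Let *r* be the response rate among dosed subjects and *n* the number randomised. With the *u* undosed scored as failures, the randomised-set rate is *r*(1 − *u*/*n*), so the fall is *r* × *u*/*n*.

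| Arm, both diseases together | Per undosed subject, r = 60% | Per undosed subject, r = 80% | u = 3, r = 60% | u = 3, r = 80% |
|---|---|---|---|---|
| Voriconazole, n = 30 | 0.60/30 = 2.0 points | 0.80/30 = 2.7 points | 6.0 points | 8.0 points |
| MK-5592, n = 60 | 0.60/60 = 1.0 point | 0.80/60 = 1.3 points | 3.0 points | 4.0 points |

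The primary endpoint is reported by disease (Day 42 for invasive, Day 84 for chronic pulmonary), so the disease-specific denominators are closer to what the ITT table will show. Per undosed subject at 60% response:

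| Disease | Voriconazole | MK-5592 |
|---|---|---|
| Chronic pulmonary aspergillosis | 0.60/25 = 2.4 points | 0.60/50 = 1.2 points |
| Invasive aspergillosis | 0.60/5 = 12 points | 0.60/10 = 6 points |

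With *u* = 0 every entry is zero.

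**The case against.** **The opportunity is narrow.** Dosing should follow randomisation the same day or nearly so, subjects have active infection, and they are in hospital at the start of treatment. Nothing in the documents suggests that refusal on learning the allocation is likely, and the undosed count may be zero. This stands. The point is that arm-related non-starting is possible, and a reader who infers that bias will occur goes beyond the text.

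**Little rests on this set.** The main objective is safety, no hypothesis is tested, the primary efficacy result is an interval by arm in the FAS, and ITT contributes point estimates only. This also stands, and it limits the severity.

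**The check is not lost.** A reader might infer that ITT adds nothing because its members match the safety set. The documents do not support that: ITT is analysed as randomised and removes the FAS diagnosis and baseline exclusions, which may be the larger selection.

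**The size is easily overstated.** A reader might take one undosed voriconazole subject to move the rate by 1/30 = 3.3 points. That is the subject's share of the denominator; the rate falls that far only if every dosed subject responds.

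**Disposition is reported anyway.** Section 8.2.5.3 displays numbers randomised and reasons for discontinuation. That would reveal a shortfall, but it is not an efficacy analysis, and a breakdown of undosed subjects by arm is not explicit.

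**Conclusion.** The concern holds as a minor one. The set called ITT is randomised and dosed, its members are those of the safety population, and no visible efficacy population contains all randomised subjects. Because allocation is known before the first dose, non-starting could depend on the arm, and the supportive analysis could not show it. The check is weakened, not lost.

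For 0 to 3 undosed subjects in one arm at 60% response, the fall is 0 to 6 points for voriconazole or 0 to 3 points for MK-5592 over both diseases together. A single invasive aspergillosis subject would move that stratum's rate by about 12 or 6 points respectively. These sizes rest on an assumed undosed count, on the planned 60:30 enrolment, on a 2:1 split within disease, and on scoring the undosed as failures.

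**What to change.** In Section 8.2.4.1, define ITT as all randomised cohort 2 subjects, analysed in the arm assigned, whether or not treatment was started. In Section 8.2.5.1.4, extend the failure rule explicitly to undosed subjects in ITT; it now speaks of missing data after treatment and does not plainly reach someone who was never treated. Report undosed subjects and their reasons by arm. The present dosed set may be kept under the name modified ITT. FAS and ASaT stay unchanged.

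The cost is about a sentence in each of the two sections and one line in the disposition table. ITT rates may fall slightly, and a refusal to start is scored as a failure, which counts against the arm where refusals occur. Showing modified ITT beside ITT lets the reader see how much of any difference comes from that scoring. If everyone is dosed, no result changes.

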## **7.3 TRIAL GOVERNANCE AND OVERSIGHT**

### **7.3.1 Clinical Adjudication Committee**

A Clinical Adjudication Committee (CAC) will evaluate the following events for the purposes of confirming them according to the criteria in Section 8.0 – Statistical Analysis Plan.

- 1) Diagnosis of deep-seated fungal infection [For subjects with all queries closed, validity of deep-seated fungal infection diagnosed by investigators is assessed]
- 2) Overall Response [For subjects with all queries closed, validity of Overall Response assessed by investigator is assessed (Overall Response, Clinical Response, Radiological Response, Mycological Response)]

All personnel involved in the adjudication process will remain blinded to treatment allocation throughout the trial. Specific details regarding endpoint definitions can be found in the Adjudication Charter.

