### 8.2.5.1.2 Secondary Efficacy Analysis

The overall response rates for invasive aspergillosis at Day 84 and for chronic pulmonary aspergillosis (chronic progressive pulmonary aspergillosis and simple pulmonary aspergilloma) at Day 42 will be provided by treatment ([Table 26](#)).

The overall response rate for all aspergillosis (invasive aspergillosis and chronic pulmonary aspergillosis are pooled) at EOT will be provided by treatment.

Clinical, radiological and mycological response rates for invasive aspergillosis and for chronic pulmonary aspergillosis (chronic progressive pulmonary aspergillosis and simple pulmonary aspergilloma) at Day 42 and Day 84 will be provided by treatment.

The overall response for the subjects with fusariosis and zygomycosis will be listed for MK-5592 treatment arm since the enrollment of these infections will be very limited.

As a sensitivity analysis, the overall response rates for invasive aspergillosis at Day 42 and for chronic pulmonary aspergillosis at Day 84 will be provided by treatment in the PP population. For the PP analysis, a subject with missing post-treatment response data or with 'unable to determine' response will be excluded. In addition, the overall response rates will be provided in the ITT population and also the overall response rates by investigators/sub-investigators will be provided in the FAS population.

Table 26 Analysis Strategy for Key Efficacy Variables

Endpoint/Variable (Description, Time Point)	Primary vs. Supportive Approach	Statistical Methods	Analysis Population	Missing Data Approach
Primary				
Overall response rates for invasive aspergillosis at Day 42 and for chronic pulmonary aspergillosis at Day 84	P	95% CI with Clopper-Pearson Exact Method	FAS	CF †
	S	Point Estimate	PP	CF †
	S	Point Estimate	ITT	CF †
	S	Point Estimate: Assessment by investigators/sub-investigators	FAS	CF †
Secondary				
Overall response rates for invasive aspergillosis at Day 84 and for chronic pulmonary aspergillosis at Day 42	P	Point Estimate	FAS	CF †
Overall response rate for all aspergillosis at EOT (invasive aspergillosis and chronic pulmonary aspergillosis are pooled)	P	Point Estimate	FAS	CF †
Clinical response rates, radiological response rates and mycological response rates for invasive aspergillosis and for chronic pulmonary aspergillosis at Day 42 and Day 84	P	Point Estimate	FAS	CF †

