#### 8.2.5.1.4 Accounting for Missing Data

For the primary analyses in FAS and ITT (overall response rates for invasive aspergillosis at Day 42 and for chronic pulmonary aspergillosis at Day 84), missing data will be imputed by a carried-forward method. Baseline values will not be carried forward and if there is no data after treatment, the missing data will be considered as failure. Data with ‘unable to determine’ will be considered as failure as well. For the overall response rates for invasive aspergillosis at Day 84 and for chronic pulmonary aspergillosis at Day 42, and also clinical, radiological and mycological response rates at Day 42 and Day 84 for both aspergillosis, the missing data will be imputed likewise.

For the analyses in PP population, a subject with missing post-treatment response data or with ‘unable to determine’ response will be excluded.

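### The one violation listed for Per-Protocol exclusion is defined by its effect on the endpoint and names no deviation, so membership can be settled with the response known

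*Combined protocol and SAP*

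**What the plan says.** The governing sentence in Section 8.2.4.1 is "The Per-Protocol population excludes patients due to important deviations from the protocol that may substantially affect the results of the primary efficacy endpoint". A list of potential violations follows, with one entry: "Subjects with cases that affect the results of the primary efficacy endpoint, confirmed by CAC". On timing, "The final determination on protocol violations, and thereby the composition of the Per-Protocol population, will be made prior to the final lock of the database", with the outcome recorded in a memo. The section does not say who makes that determination.

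The CAC also produces the endpoint. Section 7.1.2.9 makes its assessment the one used for the primary efficacy endpoint. Section 7.3.1 gives it two tasks, diagnosis and overall response; on the second, "For subjects with all queries closed, validity of Overall Response assessed by investigator is assessed". It works blind to treatment. The sponsor does not: under Section 8.2.1, "SPONSOR personnel will be aware of patient treatment assignments after each patient is enrolled".

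A further PP rule appears twice. Section 8.2.5.1.2 begins "For the PP analysis, a subject with missing post-treatment response data" and Section 8.2.5.1.4 begins "For the analyses in PP population, a subject with missing post-treatment response data"; both go on to exclude that subject, and any subject rated unable to determine. In FAS and ITT, Section 8.2.5.1.4 carries earlier post-treatment ratings forward, counts a subject with no post-treatment data as a failure, and says that unable-to-determine data "will be considered as failure as well". Table 26 lists the carried-forward method for the PP row as well.

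**The concern.** A PP rule should identify departures in conduct that can be recognised without looking at the result. The listed entry instead repeats the effect clause of the governing sentence. It does not mention eligibility, dosing, prohibited medication or visit timing, so two statisticians given the same data could not be expected to build the same PP set.

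The judgement also sits with a committee that has the response data. Blinding to treatment limits selection that differs between arms. It does not stop selection on response within each arm.

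Section 8.2.5.1.2 presents PP as a sensitivity analysis. If membership can be chosen with the response known, neither agreement nor disagreement with FAS says much about robustness. Table 26 plans a point estimate only for PP, so no interval would show how much a few exclusions matter.

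**Working it through.** **Inputs.** Section 8.2.7 gives assumed response rates of 60% and 80%, n = 60 on MK-5592 and 30 on voriconazole, and a target of 15 subjects with invasive aspergillosis (IA). Section 8.2.5.1.1 gives the Clopper-Pearson method. The documents do not say how many subjects will be excluded from PP; 1, 3 and 6 (6 is 10% of 60) are my assumptions.

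**1. The plan's own figure.** The lower 95% limit is the 2.5% quantile of Beta(x, n − x + 1). For 36/60 it is 46.54%, and for 48/60 it is 67.67%. Section 8.2.7 states 46.5% and 67.7%, so both reproduce. The plan gives no figure for PP.

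**2. Effect of exclusions.** Removing f failures and s successes from x/n gives (x − s)/(n − f − s). The rate rises if successes are under-represented among those removed (s/(f + s) < x/n) and falls if they are over-represented. Exclusion unrelated to response leaves the expected rate unchanged.

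| Start | Removed | All failures | All successes |
|---|---|---|---|
| 36/60 = 60.0% | 1 | 36/59 = 61.0% | 35/59 = 59.3% |
| | 3 | 36/57 = 63.2% | 33/57 = 57.9% |
| | 6 | 36/54 = 66.7% | 30/54 = 55.6% |
| 48/60 = 80.0% | 6 | 48/54 = 88.9% | 42/54 = 77.8% |
| 18/30 = 60.0% | 1 | 18/29 = 62.1% | 17/29 = 58.6% |
| | 3 | 18/27 = 66.7% | 15/27 = 55.6% |

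**3. By disease.** The primary rates are reported by disease, so the denominators are smaller. The targets imply 90 − 15 = 75 subjects with chronic pulmonary aspergillosis (CPA). At 2:1 that is about 50 and 25 by arm, and IA is about 10 and 5. These are enrolment targets, not FAS counts, because FAS also needs disease confirmed by the CAC. At an assumed 60% on MK-5592:

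- CPA, 30/50: removing 5 failures gives 30/45 = 66.7%; removing 5 successes gives 25/45 = 55.6%.
- IA, 6/10: removing 1 failure gives 6/9 = 66.7%; removing 1 success gives 5/9 = 55.6%.

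**4. The missing and unable-to-determine rule.** Suppose u of the FAS failures are failures only because the response was unable to determine or there were no post-treatment data. PP then gives x/(n − u), which exceeds x/n whenever x and u are above zero. From 36/60, u = 1, 3 or 6 gives 61.0%, 63.2% or 66.7%. Unlike step 2, the direction here is fixed by the text.

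**5. Table 26 against the text.** If the exclusion covers only subjects with no post-treatment rating at all, carry-forward can still apply to the others and the two statements fit. If it covers anyone missing the rating at the analysis time point, there is nothing left to carry forward, and some subjects counted as successes in FAS by carry-forward would also leave PP. The plan does not say which reading applies.

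**6. Who knows what.** Section 7.3.1 does not list PP confirmation among the CAC's tasks and refers to the Adjudication Charter only for endpoint definitions. Nothing requires the PP decision to come before, or to be masked from, the response rating.

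**The case against.** The strongest reply is that the entry cannot be read alone. The governing sentence requires an important deviation, and the entry stands in a list of potential violations, so it is an example and not a complete rule. A reader might infer that exclusion must depend on the outcome, or that this is the only PP exclusion in the plan. Neither is supported: the wording permits outcome-related exclusion without requiring it, and Sections 8.2.5.1.2 and 8.2.5.1.4 state a second exclusion.

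A reader might also infer that the entry inflates PP rates, on the ground that a deviation is more readily blamed in a non-responder. The text fixes no direction. A deviation that could produce a false success also affects the result, and removing that subject lowers the rate.

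Nor do the documents say that unblinded sponsor staff decide membership; the role is simply not named.

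The safeguards are real: the CAC is blinded to treatment, the decision precedes final lock and is documented in a memo, FAS is primary, and ITT and investigator-assessed FAS rates are reported alongside PP. No efficacy hypothesis is tested and the primary objective is safety.

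This limits the consequence. It does not supply the missing criterion, and pre-lock documentation does not mask the decision from the response.

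**Conclusion.** The point holds as a defect in a supportive analysis. The listed violation is circular, names no deviation, and is confirmed by the committee that assigns the response. PP membership can therefore be settled with the response known, and the PP rate can be biased either way. With 10% of a 60-subject arm excluded and an assumed 60% rate, the extremes are 55.6% and 66.7%. Both ends assume that every excluded subject had the same outcome, so they are bounds for illustration and not a forecast.

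The rule on missing and unable-to-determine responses is a separate matter. For subjects whom FAS counts as failures, its effect against FAS is upward; its size depends on how many there are, which the documents do not predict. The PP row of Table 26 needs reconciling with the text. No primary conclusion depends on any of this.

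**What to change.** Replace the entry in Section 8.2.4.1 with a closed list of deviations defined by conduct and drawn from data already collected. Examples are inclusion criterion 5 not met, and study-drug compliance (Section 8.2.10) below a percentage fixed in advance. Three details need settling:

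- FAS already requires disease confirmed by the CAC, so state which set PP is drawn from; if it is FAS, the inclusion criterion adds little.
- For subjects who stop permanently, Section 8.2.10.2 gives the compliance denominator as running to an earlier/later date. Choose one, so that stopping early because of failure does not itself count as poor compliance.
- Use of another systemic antifungal may follow treatment failure. Do not make it an automatic PP exclusion, or report PP with and without those subjects.

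Classify deviations from a listing that shows neither arm nor response, before the CAC ratings are merged, and name the role that decides. In Sections 8.2.5.1.2 and 8.2.5.1.4, say whether a missing response means no post-treatment rating at all or none at the time point, and align the PP row of Table 26. Report by arm how many subjects leave PP under each rule.

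The cost is a few lines of SAP text, one masked listing and less discretion at database lock.
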